A Randomized Control Trial Treating Depression With Yoga and Coherent Breathing Versus Walking in Veterans

NCT03489122

Document Date: 3-07-2022

HUMAN SUBJECTS RESEARCH PROTOCOL

Project Title: A Randomized Controlled Trial Treating Depression with Yoga and Coherent Breathing Versus Walking in Veterans

Short Title: RCT Treating Depression with Yoga or Walking in Veterans

Protocol Version and Date: Version 5 December 31, 2021

Principal Investigator (PI): [name].

Co-Investigators: [name]., Principal Investigator for the McLean Hospital.

Institution(s): The VA Bedford Healthcare System (VABHCS) is the coordinating site. The McLean Hospital, Belmont MA will be the site for MRI imaging.

1.0 OBJECTIVE AND SPECIFIC AIMS:

Aim 1: To determine in Veterans, the effectiveness of an RCT of 12-weeks of the yoga intervention versus walking intervention, with depression and mood assessed at baseline prior to randomization, and prior to and immediately following yoga or walking interventions at weeks 4, 8, and 12, and before each scan.

Hypothesis I: In this working clinical hypothesis, subjects in the yoga group will exhibit greater improvements in depressive symptoms and mood ratings over the study compared to the walking group.

Aim 2: To measure changes in thalamic GABA levels at Scans 1, 2, and 3. (3)

Hypothesis II: In this working translational hypothesis, GABA levels will increase and depressive symptoms will decrease over the course of the 12-week intervention in the yoga group compared to the walking group.

Aim 3: To examine changes in RSA acquired at baseline prior to randomization, and prior to and immediately following yoga or walking interventions at weeks 4, 8, and 12, and before each scan.

Hypothesis III: In this working translational hypothesis, RSA levels will increase and depressive symptoms will decrease over the course of the 12-week intervention in the yoga group compared to the walking group.

Exploratory Aim: If an individual has symptoms of Post Traumatic Stress Disorder (PTSD) at screening, there will be a greater decline in PTSD symptoms with treatment in the yoga compared to the walking group. The use of the 3T scanner allows the collection of pre and post exploratory data for cortical thickness, resting state, and executive function.

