2.2.m. Parasympathetic tone measured with Respiratory Sinus Arrhythmia (RSA) (Figure 5): In Study 4, RSA values were derived from an electrocardiogram (ECG) recording over a three stage protocol: 1) a 5-minute rest, 2) a 3-minute step test that removes the vagal break, and 3) a 5-minute recovery period. RSA was measured at baseline and after an intervention at weeks 4, 8, and 12. No differences between the HDG and LDG were observed for baseline or recovery RSA. A GEE analysis of changes over the 12-week intervention for the full cohort showed no RSA differences at rest ($\beta = -0.01$, $z = -0.74$, $p = 0.46$), but an increase in RSA during recovery ($\beta = 0.05$, $z = 2.12$, $p = 0.03$), consistent with the recovery stage being the best marker of tonic changes from the beginning to the end of the study. Midway through the study, an additional RSA was added pre the week-12 intervention, permitting comparison of pre- and post- week-12 intervention RSA values (n=16). Rest stage ($F_{1,15} = 11.06$, $p = 0.005$) and recovery stage changes ($F_{1,15} = 3.82$, $p = 0.07$) were significant from pre- to post- 12-week intervention. The acute changes in both rest and recovery stages observed from pre- to post-intervention, support the hypothesis that yoga acutely increases resilience measured by increased RSA in the rest and recovery stages. Tonic changes were only significant in the recovery stage, suggesting that the recovery stage is more sensitive to resilience.

2.2.n. Correlation of Thalamic GABA/Cr and RSA: Because the proposed study will use two yoga classes per week, correlational analysis of GABA and RSA was conducted on data from the LDG. Acute changes in GABA were measured at the end of the 12-week intervention from pre-yoga intervention (Scan 2) to post-yoga intervention (Scan 3). At the end of the 12-week yoga intervention, acute RSA changes were also

[figure not shown]

Figure 3: Thalamic spectra showing increased GABA (LDG Subject), Scan 1 pre-randomization to Scan 2 after a 12-week yoga intervention to Scan 3 immediately after a 90-minute yoga and breathing intervention.

[figure not shown]

Figure 4: Thalamic GABA/Cr in healthy controls and patients with MDD at baseline (Scan 1), after 12-week yoga intervention (Scan 2) and immediately after a yoga intervention (Scan 3). GABA increases in subjects with MDD, and differences between MDD and controls decreases.

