3.0 RESEARCH DESIGN AND METHODS

3.1 Drug/Device Information: NOT APPLICABLE

3.2 Type of Study: (Table 3: Individual Timeline): This is a longitudinal, efficacy randomized controlled trial (RCT). Veterans with MDD will be evaluated for eligibility and randomized to a 12-week intervention of a twice-weekly yoga and coherent breathing or walking group. As there is evidence that exercise improves mood in unipolar depression, the walking group will serve as an active control condition.(47) The policy for Common Data Elements will be incorporated into the data collection matrix. The Consolidated Standard of Reporting Trials (CONSORT) will be used to ensure the quality of reporting for this RCT.(48) The **primary dependent variable** will be changes in the Hamilton Depression Rating Scale (covering a 2 week period), and mood and anxiety scales (designed for repeated use, such that changes from pre to post intervention can be gauged), measured using valid and reliable psychological instruments obtained at screening, intervention weeks 4, 8, and 12, and before each MRS scan. The **secondary dependent variable** will be brain gamma amino-butyric acid (GABA) levels measured by magnetic resonance spectroscopy (MRS) in the left thalamus, the same region used in our prior studies.(9, 53, 65) The thalamus has the technical advantage of providing high quality spectra, has a high concentration of GABAergic neurons, and thus a high GABA signal, in which changes can be detected. The thalamus is also anatomically connected to other regions of interest. GABA levels will be measured by MRS in 3 separate scan acquisitions: before randomization (Scan 1), after 12-weeks of the yoga or walking intervention (Scan 2), followed immediately by the group assigned intervention and the final scan (Scan 3). The **third dependent variable** will be respiratory sinus arrhythmia (RSA) a component of heart rate variability (HRV) that is an accurate index of vagal influences on the heart.RSA will be measured before each scan and before and after an intervention at week 4, week 8 and week 12. Medications also are evaluated at weeks 4, 8, and 12. Two and six month follow-up phone calls will assess depression, quantity of yoga practice, and barriers to practice.

3.3.1. Sub-Study Participation: This is not a multisite study. There will be a contract with the McLean Hospital for goods and services regarding the imaging component of this study.

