3.5. Analysis Plan

3.5.1. Data Management and Analysis Plan: The study statistician and Healthcare Specialist will be responsible under a contract for data management and statistical analysis for the project. The Healthcare team will convert the REDCap shell from an earlier study and provide the monitoring reports, create of the final database. The study statistician will oversee the statistical analysis with the help of the Healthcare Specialist. Descriptive statistics will be generated for baseline data and distributions between the yoga intervention and walking intervention will be compared using two-sample t-tests and chi-square or Fisher's exact tests to assess effectiveness of randomization. Descriptive statistics include means and standard deviations for continuous variables and group sizes and proportions for categorical variables. All analyses will be performed at the $\alpha = 0.05$ level of significance. Should groups have unequal distributions at baseline, relevant variables will be incorporated in subsequent linear models that will be used to examine intervention efficacy. In order to address the study aims of assessing the relative longitudinal change independent variables between yoga intervention and walking intervention groups over time, data will be collected at four time points, pre-randomization, and at weeks 4, 8, and 12. Mixed linear model analyses will be performed focusing on the group x time interaction for the primary effects to be statistically modeled. These analyses will allow for inclusion of data at differing numbers of time points per subject if needed. We will examine different within-subject correlation structures for our interaction model and determine the optimal structure by comparing Akaike information criteria (AIC) values. The correlation structure that yields the lowest AIC will be adopted. Subjects who change antidepressant medications during the study will be included in intent to treat analysis, but will be co-varied for medication changes. Potential cohort effects will be statistically addressed by controlling for group profiles, including group size, breakdown by sex of attendees, instructor, group parameters such as individual or group sessions, and group cohesion/overlap.

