3.5.1. Data Management: The study statistician will provide leadership and expertise in data collection, management and analyses, encompassing database design, implementation of quality control procedures, technical support, and data sharing. A close interaction between data management staff and research team members will result in procedural consistency, efficiency of the study-wide systems, and ultimately produce the highest quality data. Data collection strategies will include web-based assessments using VA REDCap software. When possible, data will be collected on desktop computers, or laptops, negating the need for double entry. Electronic forms will include required fields, skip patterns, and validation resulting in more complete and "cleaner" data at capture. All participants will be assigned a unique identifier (ID) and personal identifiers that must be collected and used for consent and follow up will be stored in a separate database apart from study data. Analysed data from McLean Hospital and [name] will be provided via a VA approved system (e.g., AZURE)

3.5.1. Analysis of Hypotheses (Aim 1: Hypotheses 1. Aim 2: Hypotheses 2. Aim 3: Hypothesis 3)

Hypothesis 1. a. Depressive Symptoms: The yoga group will have decreased depressive symptoms compared to the walking group. There will be a significant within-group change (decrease) in

depressive symptoms over time, using a mixed linear model analogue of repeated measures analysis-of-variance with independent groups in MDD subjects assigned to the yoga group.

Hypothesis 1. b. Mood Scales: There will be a greater improvement in mood (as measured by the EIFI and STAI), and sleep (as measured by the PSQI) in the yoga group compared to the walking group.

Hypothesis 2. a. GABA: GABA levels will increase in the yoga group. There will be a within-group change in GABA levels over time using a mixed linear model analogue of repeated measures analysis-of-variance with independent groups in MDD subjects assigned to the yoga group.

Hypothesis 2. b. Group Differences: There will be a between-group difference in GABA levels over time using linear modeling comparing the yoga group with the walking group.

Hypothesis 3. a. RSA: There will be tonic increase in post intervention recovery RSA in the yoga but not the walking group.

Hypothesis 3. b.: There will be an increase (from baseline to end of week 12) in the difference between pre- and post-intervention in the rest and the recovery RSA in the yoga group.

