variance with independent groups. We used nQuery Advisor, version 7.0 for these computations. Using GABA level as the dependent variable of interest and employing the observation from Study 2 in which the walking intervention showed no change in GABA over the 12-week intervention, it is predicted that GABA levels will not change over time in the walking group. We hypothesize that the yoga group will show mean GABA/Cr = 0.28, 0.285, and 0.32 at the three study time points and that the walking group will show mean GABA/Cr = 0.28, 0.28, and 0.28. Assuming a common standard deviation at each time point of 0.06 and a within-subject correlation of 0.65, we will have 80% power to detect the above noted pattern of repeated mean GABA/Cr with a two-sided alpha of 0.05. With the same data configuration, we will have 85% power should the within-subject correlation be as high as 0.70.

3.5.4. Tonic changes in Recovery RSA from screening to 12 weeks: The GEE of changes in recovery RSA in the full cohort (n=27) over 12 weeks was significant in Study 4; however, only the recovery RSA values in the smaller LDG (n=14) were used for the power analysis, as this reflects the dosage that will be utilized in the proposed study. While the repeated measures ANOVA did not reach statistical significance in the LDG (screening mean = 7.7 ± 2.5 and 12 week mean = 8.2 ± 2.9 , $F_{1,12} = 1.094$, $p = 0.315$), a post hoc power analysis was conducted, which determined that the achieved effect size was $f = 0.291$, with 52% power. Based on this same small to medium effect size, an a priori power calculation that includes two groups (yoga and walking) was conducted, which determined that **n=34** subjects would be necessary to detect significant differences in RSA at effect size $f = 0.291$, with 90% power.

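### The GABA test for Hypothesis II pools the 12-week change with the response to one further session, and the RSA hypotheses 3a and 3b lack matching baseline readings.

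*Protocol*

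**What the plan says.** **GABA.** Hypothesis II (protocol section 1.0) predicts that "GABA levels will increase and depressive symptoms will decrease over the course of the 12-week intervention in the yoga group", compared with walking. Section 3.2 places Scan 1 before randomization and Scan 2 after the 12 weeks, "followed immediately by the group assigned intervention and the final scan (Scan 3". Hypotheses 2a and 2b (section 3.5.1) refer to change over time without naming scans; 2b reads "There will be a between-group difference in GABA levels over time using linear modeling comparing the yoga group with the walking group". The general method, in both protocol section 3.5.1 and SAP section D.17, is: "Mixed linear model analyses will be performed focusing on the group x time interaction for the primary effects to be statistically modeled". The general time points are not the scan times: "data will be collected at four time points, pre-randomization, and at weeks 4, 8, and 12". Section 3.5.3 gives GABA three time points: "We hypothesize that the yoga group will show mean GABA/Cr = 0.28, 0.285, and 0.32 at the three study time points". Walking is assumed flat at 0.28. The power stated for this pattern is 80%.

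The protocol separates the two kinds of change elsewhere. Section 2.2.d calls Scan 2 minus Scan 1 tonic and Scan 3 minus Scan 2 acute, for mood scores. Section 2.2.n does the same for the acute GABA change: "Acute changes in GABA were measured at the end of the 12-week intervention from pre-yoga intervention (Scan 2) to post-yoga intervention (Scan 3".

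**RSA.** Hypothesis 3a reads "There will be tonic increase in post intervention recovery RSA in the yoga but not the walking group". Hypothesis 3b predicts that, in the yoga group, the pre/post-session difference in rest and recovery RSA grows from baseline to the end of week 12. Table 3 schedules one reading before Scan 1 (RSA 1), pre/post pairs at weeks 4, 8 and 12 (RSA 2 to 7), and readings before Scans 2 and 3 (RSA 8 and 9).

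**The concern.** A group-by-time test over three scans asks whether the arms differ in any way across those scans. It cannot tell a change built up over 12 weeks from a change produced by the session just before Scan 3. Under the planning assumptions most of the expected difference is of the second kind. A significant result could then be reported as support for a 12-week effect that the data do not show.

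For RSA, two analysts could follow the plan in good faith and use different readings. Hypothesis 3b cannot be computed as written, because the schedule has no pre/post pair at baseline. If the phrase post intervention in hypothesis 3a means after a session, its baseline is of a different kind, since RSA 1 follows no session. A change from RSA 1 to a post-session reading then mixes tonic and acute change under the label tonic.

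**Working it through.** **Inputs (section 3.5.3):** 26 per arm; yoga means 0.28, 0.285, 0.32; walking means 0.28 throughout; SD 0.06; within-subject correlation 0.65; two-sided alpha 0.05.

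**Step 1: reproduce the stated power.** The yoga-minus-walking differences are 0, 0.005 and 0.040, with mean 0.015. The deviations are -0.015, -0.010 and 0.025, and their squares sum to 0.00095. The noncentrality is (n/2) × sum of squares / [SD² × (1 − correlation)] = 13 × 0.00095 / (0.0036 × 0.35) = 9.80. With 2 and 100 degrees of freedom, power is 79.5%. At correlation 0.70 it is 85.6%. The stated 80% and 85% both reproduce.

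**Step 2: split the pattern.** Of the 0.040 difference at Scan 3, 0.005 arises between Scans 1 and 2, and 0.035 between Scans 2 and 3. The SD of a change between two scans is 0.06 × √(2 × 0.35) = 0.0502. The standard error of the between-arm difference is 0.0502 × √(2/26) = 0.0139. Two-sample t tests with 50 degrees of freedom give:

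| Contrast | Difference | Power, correlation 0.65 | Power, correlation 0.70 |
|---|---|---|---|
| Scan 2 − Scan 1 | 0.005 | 6.4% | 6.7% |
| Scan 3 − Scan 2 | 0.035 | 69.3% | 75.9% |
| Scan 3 − Scan 1 | 0.040 | 80.4% | 86.1% |

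Section 3.3.2.2 gives 56 subjects with usable scans, or 28 per arm. At 28 per arm and correlation 0.65, the three contrasts have about 7%, 73% and 83%, and the three-scan test about 83%.

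**Step 3: find where the 80% comes from.**
- No 12-week effect, session effect 0.035 only (differences 0, 0, 0.035): noncentrality 8.43, and the three-scan test is significant 72.8% of the time.
- 12-week effect 0.005, no session effect (differences 0, 0.005, 0.005): noncentrality 0.17, power 6.3%.

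**Step 4: see what a significant three-scan test would imply.** In 20,000 simulated trials under the planning means, the three-scan test was significant in 79.2%. Among those, Scan 2 − Scan 1 was also significant in about 8%, and Scan 3 − Scan 1 in about 94%.

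**Step 5: find what the trial could detect over 12 weeks.** At 26 per arm, a Scan 2 − Scan 1 difference of about 0.040 has 80% power. The assumed 0.005 would need about 1,584 per arm.

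**RSA: passages side by side.**
- Hypothesis 3b needs a pre/post difference at baseline. Sections 3.2, 3.3.2.18 and 3.4.2.4 and Table 3 give one reading before Scan 1 and put the first pair at week 4.
- Hypothesis 3a calls a post-intervention reading tonic. Section 2.2.m says that Study 4 took RSA at baseline and after a session at weeks 4, 8 and 12, with a pre-session reading added only at week 12 and only midway through. The 12-week mean of 8.2 behind n = 34 in section 3.5.4 therefore appears to be post-session. Section 3.5.5 gives week-12 recovery means of 6.7 before and 8.1 after a session. The low-dose group's screening mean in section 3.5.4 is 7.7. The subsets differ, so no matched tonic estimate can be formed.
- Section 3.4.2.4 counts 9 recordings, and section 3.3.2.18 describes each as rest, step and recovery. Section 4.6.1.6 counts 7 step tests. It is unclear which recordings have a recovery phase.

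No error rate is given for RSA, because the documents lack the figures needed.

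**The case against.** The strongest reply on GABA is that nothing in section 3.5.3 is miscalculated. The 80% is claimed for the three-scan pattern, and that is correct. A reader might infer from the 6% that the protocol promised 80% for the 12-week contrast; it did not. A reader might also infer that Scan 2 minus Scan 1 is plainly the test of Hypothesis II. The documents do not settle this. Aim 2 names all three scans, and section 2.2.j describes Scan 3 as post 12-week intervention when testing pilot GABA from Scan 1. On that reading power is 80.4%. This stands, and it limits the point to an undefined contrast. It does not remove the point, because Scan 3 minus Scan 1 still contains the session response, which sections 2.2.d and 2.2.n treat separately.

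The four general time points carry little weight as a complaint, since section 3.5.3 gives GABA its own three.

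On RSA, a reader might infer that hypotheses 3a and 3b name no readings at all. That goes too far: 3a gives the stage and the timing, 3b gives both stages and its end points, and section 3.5.4 is headed screening to 12 weeks. A reader might also see a contradiction with section 3.3.2.11, which mentions pre and post data for on-site visits that include randomization. That passage does not mention RSA, and can be read as equipment at randomization and paired data at weeks 4, 8 and 12. Finally, replacing the post-intervention reading in 3a with a pre-session one would change the hypothesis, so the pre-session estimate belongs beside it.

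**Conclusion.** The point holds in this form: the contrast that decides Hypothesis II is undefined, and the planned test pools two different effects. Depending on the contrast chosen, power is about 6%, 69% or 80%, and a session effect alone would make the three-scan test significant about 73% of the time. These figures rest on the protocol's own means, SD and correlation, equal correlation between all scan pairs, and 26 per arm; 28 per arm or correlation 0.70 does not change the picture. They show what the planning assumptions imply, not what the trial will find.

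For RSA, two gaps remain: hypothesis 3b has no scheduled baseline pair, and the tonic claim in 3a compares a post-session reading, on the likelier meaning, with a baseline that follows no session. The depression outcome is not affected. The change should be made before analysis.

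**What to change.** 1. **GABA.** From the same mixed model with time as a categorical factor, prespecify yoga-minus-walking contrasts for Scan 2 − Scan 1 (12-week, tonic) and Scan 3 − Scan 2 (acute). State which contrast decides Hypothesis II. Do not report a significant three-scan or Scan 3 − Scan 1 result by itself as a 12-week effect. Keep the 80% labelled as power for the three-scan pattern, and add about 6%, 69% and 80% for Scan 2 − Scan 1, Scan 3 − Scan 2 and Scan 3 − Scan 1.
2. **Hypothesis 3b.** Restate it as the change in post-minus-pre RSA from week 4 (RSA 3 − RSA 2) to week 12 (RSA 7 − RSA 6), noting that week 4 already follows some training. If a first-session pair is in fact collected, add it to the schedule and use it as the baseline.
3. **Hypothesis 3a.** Name the readings. If post-session RSA 7 is kept, state that RSA 1 to RSA 7 mixes tonic and acute change. Report RSA 1 to pre-session RSA 6 alongside as the tonic estimate, noting that n = 34 was not derived for it.
4. **Recordings.** Reconcile the 7 step tests in section 4.6.1.6 with the 9 recordings in section 3.4.2.4, so that it is clear which have a recovery phase.

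The cost is wording in the hypotheses and SAP; all three scans and RSA 1 to 7 are already scheduled. The plan would have to show that its 12-week GABA contrast has low power on its own means, and the restated 3b would miss any change before week 4.

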- (10) **Pittsburgh Sleep Quality Index (PSQI)** is a self-administered instrument that assesses 9 factors of sleep over a month period, providing a composite score, with higher scores indicating poorer sleep quality.(71)
- (11) **Timeline Follow Back (TLFB)** will be used to assess alcohol consumption for three months prior to screening.(72) A format similar to the TLFB will be used for nicotine consumption.
- (12) **Brief Pain Inventory**, an eleven point Likert Scale of pain intensity will be used to assess pain over the last 24 hours.
- (13) **Stroop Color-Word Test** is a selective attention and inhibitory cognitive control task.(74)

Individual Time Line	Table 3: Individual Time Line and Collection of Dependent Variables		
	Aim 1	Aim2	Aim 3
Individual Time Line	Depression Scales	Mood Scales	GABA RSA
Telephone Screen			
Screening Session	HDRS/BDI-II 1		
3T Brain Scan			
MRS Imaging Session 1			
Pre Scan 1 Measures	HDRS/BDI-II 2	EIFI & STAI 1	RSA 1
MRS Scan 1(Baseline)			GABA 1
Randomization			
Week 4			
Pre-Week 4 Evaluation		EIFI & STAI 2	RSA 2
Week 4 Intervention			
Post-Week 4 Evaluation	HDRS/BDI-II 3	EIFI & STAI 3	RSA 3
Week 5-7 Intervention			
Week 8			
Pre-Week 8 Evaluation		EIFI & STAI 4	RSA 4
Week 8 Intervention			
Post-Week 8 Evaluation	HDRS/BDI-II 4	EIFI & STAI 5	RSA 5
Week9-11 Intervention			
Week 12			
Pre-Week 12 Evaluation		EIFI & STAI 6	RSA 6
Week 12 Intervention			
Post-Week 12 Evaluation	HDRS/BDI-II 5	EIFI & STAI 7	RSA 7
MRS Imaging Session 2			
Pre Scan 2 Evaluation	HDRS/BDI-II 6	EIFI & STAI 8	RSA 8
Scan 2			GABA 2
Interscan Intervention			
Pre-Scan 3 Evaluation		EIFI & STAI 9	RSA 9
Scan 3			GABA 3
Follow-Up 2 month	HDRS/BDI-II 6	EIFI & STAI 10	
Follow-Up 6 month	HDRS/BDI-II 6	EIFI & STAI 11	

(14) **Digit Symbol Substitution Test (DSST)** is one of the frequently used tests to measure psychomotor slowing, and is clinically sensitive because it makes demands on several processes, including perception, working memory, sustained attention and visuomotor co-ordination (Wechsler 1997).

(15) **Child Trauma Questionnaire (CTQ)** is a self-report measure of childhood trauma. (73) This scale will be given during the Week 4 evaluation at the end of the session.

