3.4.2.4. RSA Data: Electroencephalogram (ECG) data will be collected 9 times during the study, three times at the McLean Hospital prior to each scan and before and after evaluations at weeks 4, 8, and 12 at the ENRMH. This data will be collected using a hand held device, a Bittum Faros, and transferred to a VA laptop computer where it will be processed and blinded before being sent through secure electronic means to [name], Co-Investigator for analysis. [name] will then send the analyzed data back for incorporation into the final database. The software that will be used to transfer the data from the Bittum Faros will be put on the VA computers by the VABHCS Information Technology (IT) staff.

3.4.2.5. Storage: Data will be stored in the REDCap database that will be created within the VA system, scan data will be stored in the locked McLean hard drives which are backed up regularly, the original ECG recordings will be stored on the VA network in a designated file. The ECG data sent to [name] will not contain HIPPA identifiers, when the data is returned it will be saved on a VA computer. The final data set will incorporate REDCap, imaging and RSA data. The management of the REDCap database and merging of the other databases into the final data will be done by the study statistician and Healthcare Specialist in accordance with VA regulations. The desktop computer will be stored in the Project Manager's Office, The laptops will be stored in [name] and the research staff's office and will be taken to the McLean Hospital as needed. [name] will also be Teleworking such that she will take her computer with her to her home and appointments, this computer will be encrypted. Papers with personal information will be kept in the offices of [name], the Project Manager and research staff in locked filing cabinets when not in use. Data regarding scan acquisition will be kept in a locked filing cabinet at the McLean Hospital or on secure servers. A Final Copy of the Database will be stored at the VABHCS on the VA network. One copy will be stored on the PI's VA laptop, a third copy will be provided to the study statistician. The database is owned by the VA.

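### Hypothesis 3.b needs a baseline pre/post RSA pair that is not collected, 3.a and 3.b do not state the planned arm contrast, and Aim 1's .02 sizing level is missing from the analysis rule

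*Protocol*

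**What the plan says.** **Planned test.** Protocol 3.5.1 (Data Management and Analysis Plan) states: "Mixed linear model analyses will be performed focusing on the group x time interaction for the primary effects to be statistically modeled". SAP D.17 has the same rule. Both set alpha at 0.05 for all analyses and give no multiplicity adjustment.

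**Aim 3.** Hypothesis III in section 1.0 is comparative: "RSA levels will increase and depressive symptoms will decrease over the course of the 12-week intervention in the yoga group compared to" walking. In 3.5.1 (Analysis of Hypotheses), 3.a reads "There will be tonic increase in post intervention recovery RSA in the yoga but not the walking group". Hypothesis 3.b reads "There will be an increase (from baseline to end of week 12) in the difference between pre- and post-intervention", for rest and recovery RSA, in the yoga group only. Exploratory 4.a (depressive symptoms by antidepressant use) has the same one-arm-but-not-the-other form as 3.a.

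**Other aims.** Hypothesis 1.a opens with a comparison of the arms, then adds "There will be a significant within-group change (decrease) in" depressive symptoms for the yoga group. Hypothesis 1.b is comparative. Hypothesis 2.a is within yoga, and 2.b supplies the contrast: "There will be a between-group difference in GABA levels over time using linear modeling comparing the yoga group with the walking group". RSA has no counterpart to 2.b.

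**RSA schedule.** Section 3.4.2.4 counts nine recordings: "three times at the McLean Hospital prior to each scan and before and after evaluations at weeks 4, 8, and 12". Table 3 and section 3.3.2.18 agree.

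**Sizing levels.** Section 3.5.2 uses .02 for BDI-II, STAI and EIFI and gives multiplicity as the reason. Section 3.5.3 (GABA) uses 0.05, 3.5.4 (tonic RSA) states no level, and 3.5.5 (acute RSA) uses .01 without giving a reason.

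**Primary scale.** Section 3.2 names the Hamilton scale together with mood and anxiety scales. Section 3.4.2.1 names the Hamilton scale alone. Section 3.5.2 sizes on BDI-II, STAI and EIFI.

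**The concern.** Four things do not connect.

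1. Hypothesis 3.b refers to a baseline value that the schedule does not produce. Whoever analyses it must choose a substitute, possibly after seeing data.
2. Hypotheses 3.a and 3.b describe what happens within arms, while the aim and the model concern a difference between arms. Nothing says which result decides an aim. Section 3.2 treats walking as an active control, so improvement in both arms is plausible, and a within-arm reading would then not show superiority over walking.
3. The allowance for several mood and depression scales was built into Aim 1's sample size but is absent from the rule by which those scales will be tested.
4. The scales that were sized are not the ones named as primary, so it is unclear which tests the allowance covers.

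**Working it through.** **1. Can 3.b be computed?** RSA recordings in Table 3, in order:
- RSA 1: before Scan 1, before randomization, single recording.
- RSA 2 and 3: before and after the week 4 session (first pair).
- RSA 4 and 5: before and after the week 8 session.
- RSA 6 and 7: before and after the week 12 session.
- RSA 8 and 9: before Scans 2 and 3, separated by the row "Interscan Intervention" (a further pair after week 12).

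The count is 3 + 6 = 9, as section 3.4.2.4 says. Let D be the post value minus the pre value. D exists at weeks 4, 8 and 12 and around the interscan session. It does not exist at baseline, so D(week 12) minus D(baseline) is undefined.

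**2. Reproducing the stated sizes.** Two-occasion repeated-measures F test: lambda = f^2 x N x 2/(1 - r), with 1 and N - k degrees of freedom (k = number of groups). The correlation r is not stated; r = 0.5 is assumed unless noted.
- Aim 1 (f = .281, N = 35): lambda = 0.07896 x 35 x 4 = 11.05. Power at .02 is 80.6% (k = 1) or 80.5% (k = 2), against the stated 81%. At .05 it is 89.8% (k = 1).
- Same inputs with r = 0.35 and alpha .05: lambda = 8.50, power 80.9% (k = 1). The stated pair therefore does not identify alpha by itself.
- Tonic RSA (f = .291, N = 34): lambda = 11.52, power 90.8-90.9% at .05 and 82% at .02. The stated 90% fits 0.05.
- Two-group interaction (k = 2), smallest even total N for 90% power: 34 for tonic RSA at .05 (90.8%; 32 gives 89.0%); 10 for acute rest RSA, f = .858, at .01 (95.1%; 8 gives 81.6%); 20 for acute recovery RSA, f = .504, at .01 (93.4%; 18 gives 89.4%). All three match the protocol.

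**3. Size of the lost multiplicity allowance (illustration).** Three tests, one per scale named in 3.5.2, no true effects:
- Independent: 1 - 0.95^3 = 14.3%, and 1 - 0.98^3 = 5.9%.
- Correlation 0.7 between test statistics (assumed; simulated, 600,000 draws): 10.9% at .05 and about 4.6% at .02.

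**4. What a within-arm reading of 3.a would do.** Suppose, as an assumption, that 3.a is met when yoga rises significantly and walking does not, each at two-sided .05 with 34 per arm. Let dz be the true change divided by its SD, equal in both arms. Let p be the chance that one arm shows a significant rise (noncentral t, 33 df, noncentrality dz x sqrt(34)). The arms are independent, so the chance that 3.a is met is p(1 - p).
- dz 0: .025 x .975 = 2.4%
- dz 0.1: .082 x .918 = 7.5%
- dz 0.2: .204 x .796 = 16%
- dz 0.28: .354 x .646 = 23%
- dz 0.35: about .5 x .5 = 25% (maximum)
- dz 0.58: .907 x .093 = 8%

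With equal change in both arms, the two-sided interaction test favours yoga 2.5% of the time throughout.

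**The case against.** The best defence is that the protocol and SAP already plan group x time for the aims and that Hypothesis III is comparative. On that view 3.a and 3.b are predicted patterns, not decision rules. This largely stands. A reader might infer from the wording of 3.a that Aim 3 will be decided by separate p-values in each arm, with up to a 25% false claim. The documents state no such rule. They also give no walking-arm RSA figure, so equal change is only a scenario, and with no change in either arm there is no inflation. What remains is that RSA alone among the three aims has no between-arm statement in the hypothesis list.

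A reader might also infer that the whole trial was sized at .02 or .01. It was not. GABA uses 0.05 and tonic RSA reproduces at 0.05. Only Aim 1's level is tied to multiplicity, and the acute RSA sizes (10 and 20) do not set the trial's 70 completers. Testing at a looser level than the sizing level does not cost power; it removes an error allowance.

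Nor do the stated sizes show that only within-arm tests were intended: sections 3.5.4 and 3.5.5 refer to two groups, and a two-group interaction calculation fits. The separate caveat is that its effect size comes from change in yoga-only pilot subjects, not from an arm difference.

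The three-scale family is a simplification. EIFI has four subscales, 1.b adds sleep, and the Hamilton scale is not among the three.

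On 3.b there is little to say in defence. Section 3.3.2.11 loosely links the in-person randomization visit with pre and post data, but no RSA recording is listed there.

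**Conclusion.** The point holds in four limited parts.
- Hypothesis 3.b cannot be computed as written. This needs no assumption.
- Aim 1's .02 is not carried into the analysis rule. The illustrative cost is a family error of about 11-14% instead of 5-6%, for three tests with correlation between 0 and 0.7.
- Hypotheses 3.a, 3.b and exploratory 4.a do not state the arm contrast that the plan otherwise intends. This is a defect of wording and of linkage to the model. The 2% to 25% range applies only under a within-arm rule that the documents do not adopt and equal change in both arms.
- Sections 3.2, 3.4.2.1 and 3.5.2 disagree on the primary scale or scales.

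These should be fixed before analysis. They do not show that the planned group x time test is wrong.

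**What to change.** 1. Restate 3.b as the yoga-versus-walking difference in how the pre-to-post RSA change grows from week 4 to week 12, for rest and recovery. Say whether the interscan pair (RSA 8 and 9) is used.
2. Restate 3.a and 4.a as group x time contrasts. State that the between-arm test decides Aims 1 to 3 and that within-yoga changes are descriptive.
3. Carry .02 into Protocol 3.5.1 and SAP D.17 for Aim 1 and list the tests it covers, or restate the 3.5.2 sizing at 0.05. Give a reason for the .01 in 3.5.5 and carry it through, or align it with 0.05.
4. Name the primary scale or scales once, and make sections 3.2, 3.4.2.1 and 3.5.2 agree.

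**Cost.** Text changes in the protocol and SAP; no new visits or data. Three consequences should be accepted openly. A change within yoga alone can no longer support a success claim. Starting 3.b at week 4 misses any change in the acute response before then. Section 3.5.5 sizes the week 12 acute change, so no sample size is given for its growth over time.
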